Purpose of clinical trial	To explore the distribution of novel optical coherence tomography (OCT) parameters in patients with different subtypes of dementia, MCI patients with or without positive amyloid scan and cognitively intact older adults and to evaluate the diagnostic value of these parameters.
Primary objective	Relative distribution of retinal and choroidal thickness, flow index and vessel density in the different subpopulations.
Secondary objective (s)	
- Diagnostic performance of the aforementioned parameters to distinguish the different subpopulations.- The association between these parameters and the presence of cardiovascular risk factors.
Trial Design	Observational, cross-sectional
Endpoints	The diagnostic performance of retinal and choroidal thickness, flow index and vessel density to classify between amyloid positive vs amyloid negative

	controls, amyloid-positive vs amyloid negative MCI, AD and DLBD.
Sample Size	
85
 
 -15 amyloid-positive and 15 amyloid-negative cognitively intact controls (55-80 years) - 15 amyloid-positive and 15 amyloid-negative MCI patients - 15 patients in the dementia stage of AD - 10 patients with LBD
Summary of eligibility criteria	
Confirmed diagnosis of MCI, AD, LBD or absence of dementia (cfr 4.1 inclusion criteria)
 
Capable and willing to participate

Maximum duration of treatment of a Subject	/
Version and date of final protocol	V1.1 17-04-2016
Version and date of protocol amendments	

2. Background and rationale

Being a direct extension of the central nervous system and the only place in the human body where the vessels of the central circulation can be visualized directly, the eye provides a unique window to investigate the central circulatory system. Several studies have demonstrated that retinal blood vessels show structural and functional alterations in patients with dementia. These measurements are based on fundus pictures and are hence limited to the larger retinal vessels.

Until recently, intravenous injection of a contrast agent was necessary to visualize the retinal microvasculature in detail. While indispensable for the diagnosis of some ocular vascular diseases (arterial/venous occlusion, neovascularization,...) the invasiveness of fluorescein angiography (and the risk of an allergic reaction) limits its use as a screening tool to detect alterations in the microvascular network of the retina and choroid.

Optical coherence tomography (OCT) is a non-invasive diagnostic tool capable of generating cross-sectional coupes of the retina and choroid. Novel algorithms allow to render a 3-dimensional model of the ocular microcirculation based merely on the motion contrast of the circulating blood. Since OCT is fast, easy to perform and completely non-invasive, this technique lends itself for screening purposes.

The proposed study aims to investigate whether retinal or choroidal vascular parameters measured using OCT could be useful to identify different subpopulations of cognitive intact, MCI and dementia patients.

Figure 1. OCT camera

[figure not shown]

Figure 2. OCT angiography

3. Trial objectives and Design

In this observational study, we aim to evaluate whether changes in the retinal and choroidal circulation, as assessed by OCT are correlated with the degree and subtype of dementia and with the presence or absence of a positive amyloid scan.

For this purpose, patients with established AD and LBD, as well as amyloid positive and amyloid negative MCI and aged matched cognitively intact patients will be included in this cross-sectional study.

4. Selection and withdrawal of subjects

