4.1 Inclusion criteria

- Cognitively intact healthy controls will be recruited from an ongoing community-recruited longitudinal cohort of cognitively intact older adults (55-85 years, S51125) who all have undergone amyloid PET at the baseline visit in the context of study S51125. Half of the subjects will be amyloid-positive and half will be amyloid-negative. In the context of study S51125 these subjects receive two-yearly neuropsychological assessment.
- MCI patients (Petersen et al., 2004 criteria) will be recruited from an ongoing memory-clinic recruited longitudinal cohort of patients with amnestic mild cognitive impairment who participate in study S55892. All subjects have undergone an amyloid PET at the baseline study in the context of study S55892. Half of the subjects will be amyloid-positive and half will be amyloid negative.
- Clinically probable AD subjects (NINCDS-AIREN criteria) will be recruited from the memory clinic UZ Leuven (MMSE 12-28). Subjects will be recruited only if they are capable of providing written informed consent.
- Clinically probable LBD (McKeith et al. criteria, 2005) will be recruited from the memory clinic UZ Leuven (MMSE 12-28). Subjects will be recruited only if they are capable of providing written informed consent.
- Capable and willing to participate

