8.1 Sample size

As of now, there is no data available on the distribution of flow index or vessel density in the population. This exploratory study is aimed to provide data on the distribution of these parameters in the healthy and diseased population. For this purpose, we will recruit 15 amyloid-positive and 15 amyloid-negative cognitively intact controls, 15 amyloid-positive and 15 amyloid-negative MCI, 15 clinically probable AD in an early stage and 10 clinically probable LBD.

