8.2 Analysis

Demographics and measured parameters will be analyzed with descriptive statistics (mean \pm standard deviation). Image analysis for the OCT will be performed with the software provided by the manufacturer. To evaluate the diagnostic performance of these parameters in distinguishing between subcategories, 'receiver operating characteristic' (ROC) curves with 'area under the curve' (AUC) analysis will be used. Logistic regression models will be used to assess the association between retinal/choroidal vascular parameters and cardiovascular risk factors. Statistical significance will be based on two-sided P-values of <0.05 . All statistical analyses will be performed using SPSS 20.0 for Mac (SPSS Inc., Chicago, IL, USA).

9. Quality assurance

To assure maximal quality and reproducibility, the trial protocol will be followed rigorously.

10. Direct access to source data and documents

Demographics and disease-related parameters (functional assessment, biochemistry and imaging) will be retrieved from the electronic medical health record. When not available, additional tests will not be performed.

11. Ethics and regulatory approvals

The trial will be conducted in compliance with the principles of the Declaration of Helsinki (2008), the principles of GCP and in accordance with all applicable regulatory requirements. This protocol and related documents will be submitted for review to Ethics Committee of the University Hospitals Leuven.

The Study will be conducted only on the basis of prior informed consent by the Subjects to participate in the Study. We shall obtain a signed informed consent form (ICF) for all patients prior to their enrollment and participation in the Study in compliance with all applicable laws,

regulations and the approval of the (local) Ethics Committee, if required. We shall retain such ICFs in accordance with the requirements of all applicable regulatory agencies and laws.

12. Data Handling

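### The synopsis caps controls at 80 years but Section 4.1 carries no such cap, and nothing in 4.1 or 8.2 delivers or replaces the age matching promised in Section 3

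*Protocol*

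**What the plan says.** The Sample Size row of the protocol synopsis describes this study's controls as "15 amyloid-positive and 15 amyloid-negative cognitively intact controls (55-80 years"). The eligibility row of the same synopsis gives no ages and sends the reader onward: "absence of dementia (cfr 4.1 inclusion criteria").

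The only age figure in Section 4.1 is in the control bullet, where controls come from an "ongoing community-recruited longitudinal cohort of cognitively intact older adults (55-85 years, S51125"). Section 4.2 has no age exclusion, and Section 8.1 repeats the group sizes without ages. No age range is given for the MCI, AD or LBD groups.

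Section 3 states that "aged matched cognitively intact patients will be included". Section 8.2 plans ROC curves with AUC for diagnostic performance and mentions no adjustment for age.

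**The concern.** Two separate matters meet here.

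- **Eligibility.** Someone recruiting from Section 4.1 finds no ceiling of 80, while someone reading the synopsis does. A cohort member aged 81-85 meets everything in 4.1 and 4.2 but lies outside the synopsis range.
- **Age comparability.** The protocol treats age matching as a design feature but includes no step that achieves it. The control range is the only age limit written anywhere, and a range does not amount to matching. If retinal or choroidal parameters change with age, an unadjusted AUC for controls against patients counts any difference in age as discrimination by disease. The study could then report diagnostic value that partly reflects who was older.

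**Working it through.** **Stated total.** The group sizes sum to 15 + 15 + 15 + 15 + 15 + 10 = 85, as the synopsis says. The protocol gives no power, effect size or SD, so no power figure depends on the age range.

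**The two ranges side by side.**

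| Place | Range | What it describes |
|---|---|---|
| Synopsis, Sample Size | 55-80 (26 whole years) | This study's controls |
| Section 4.1, control bullet | 55-85 (31 whole years) | Source cohort S51125 |

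The difference is exactly the ages 81, 82, 83, 84 and 85.

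**Size of the 80-versus-85 difference.** The documents give no age distribution and no age effect, so both are assumed.

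1. With ages uniform over each range, the control means are (55 + 80)/2 = 67.5 and (55 + 85)/2 = 70.0, a shift of 2.5 years.
2. With an assumed age effect of 0.2-0.4 SD per decade, the standardised shift is d = 0.25 × 0.2 = 0.05 to 0.25 × 0.4 = 0.10.
3. For two normal groups with equal SD and no disease effect, AUC = Φ(d/√2). This gives 0.514 for d = 0.05 and 0.528 for d = 0.10, against 0.50 with no age difference.
4. With 15 per group, the null standard error of an AUC is √[(15 + 15 + 1)/(12 × 15 × 15)] = √(31/2700) ≈ 0.107. The shift is 0.014/0.107 ≈ 0.13 to 0.028/0.107 ≈ 0.26 of one standard error.

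**Size of a general failure to match.** At the same assumed age effect, a 5-year gap in mean age (d = 0.1-0.2) gives an AUC of 0.528-0.556, and a 10-year gap (d = 0.2-0.4) gives 0.556-0.611. These figures illustrate unmatched groups. They are not a consequence of moving the ceiling from 80 to 85.

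**Which comparisons are exposed.** The synopsis endpoint and Section 5 name amyloid-positive against amyloid-negative controls, the same contrast within MCI, and AD and DLBD. The first lies within controls and the second within MCI, so an age gap between controls and patients enters neither. Only comparisons of controls with a patient group are exposed.

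**The case against.** A reader might infer that people aged 81-85 are both admitted and excluded. The text does not prove that. In Section 4.1 the figure 55-85 belongs to the source cohort, and in the synopsis 55-80 belongs to this study's controls. Taking the 55-80 subset of a 55-85 cohort satisfies both. What stands is that the protocol never says this is intended, and the section to which the synopsis refers for eligibility has no ceiling of 80.

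A reader might also infer that the mismatch itself undermines the matching, or that it could push an AUC towards 0.6. Neither follows. A ceiling does not create matching, and reconciling 80 with 85 would not define it. The larger AUC figures need a 5- to 10-year gap in mean age, which the mismatch alone does not produce. The direction is also unknown, because admitting older controls could narrow a gap to the patients.

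Nor do the documents make controls the reference group for every ROC curve, and the primary objective is the relative distribution of the parameters.

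Finally, the choice of covariates is often left to an SAP, and one may exist. That is fair as to the form of the adjustment. The age range and the way controls are chosen are recruitment matters, which an SAP written for the analysis cannot settle.

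**Conclusion.** The point holds as a minor one. The two age statements for controls need reconciling, because eligibility at 81-85 is unsettled; the documents do not show which upper limit was intended. Separately, the matching promised in Section 3 has no selection step in 4.1, and 8.2 as written has no age adjustment to stand in for it.

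The effect of the 80-versus-85 difference alone is about 2.5 years in mean control age and about 0.01-0.03 in AUC. That rests on uniform ages, an age effect of 0.2-0.4 SD per decade and normal groups with equal SD, none of which comes from the protocol. It is well below one standard error at 15 per group. The total of 85 does not change, and the study is described as exploratory.

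**What to change.** - **Age range.** State one control age range in both the synopsis and Section 4.1. If the controls are a subset of cohort S51125, say so in 4.1.
- **Selection.** Add a line to 4.1 that controls are chosen from the cohort with regard to the patients' ages, as far as the 15/15 amyloid split allows, and name the patient group or groups that serve as the target. A strict matching scheme in narrow age bands is not advised: the documents do not show that enough amyloid-positive controls exist in each band.
- **Analysis.** In the control-versus-patient comparisons, adjust for age, for example with a covariate-adjusted ROC curve or logistic models that include age, and report this beside the unadjusted AUC.

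**Cost.** The change is a short wording amendment, some restriction in the choice of controls, a little more analysis, and slightly less precision with 10-15 per group. Age is among the demographics already collected, so no new data are needed.

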4.3 Expected duration of trial

10 minutes per person

5. Trial Procedures

1. Informed consent: AD en LDB patients will be accompanied by a personal study partner who will verify and sign whether the purpose, course and voluntary nature of the trial has been explained to the patient in a clear and understandable language, prior to signing the informed consent.

2. Medical questionnaire assessing personal medical history of cardiovascular diseases and cardiovascular risk factors. When necessary, the Electronic Health Record as well as treating physicians might be consulted to complete the questionnaire.
3. Basic non-invasive ophthalmic examination: visual acuity, slit lamp assessment of the anterior and posterior segments, lens grading and non-dilated fundus photography
4. OCT: Macula centered cube followed by optic disc centered cube, for both eyes
Each scan takes approximately 2.5 seconds.
5. Retinal and choroidal thickness and motion decorrelation will be measured using the provided software.
6. The diagnostic performance of these OCT parameters to classify between amyloid positive vs amyloid negative controls, amyloid-positive vs amyloid negative MCI, AD and DLBD will be evaluated.

6. Assessment of efficacy

/

7. Assessment of Safety

The power and frequency of the light source used by the fundus camera and by the spectral-domain OCT are completely harmless for the human retina and cause no subjective discomfort. The OCT device uses a faint light at the near-infrared spectrum that can barely be perceived by the human eye. Pupillary dilatation is not required.

8. Statistics

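### Age matching is stated only for the cognitively intact group, and section 8.2 names no covariate for the ROC analysis; an age-adjusted AUC beside the raw one would be a cheap improvement

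*Protocol*

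**What the plan says.** **Matching.** Age matching appears once, in section 3: "amyloid positive and amyloid negative MCI and aged matched cognitively intact patients will be included in this cross-sectional study". It qualifies the cognitively intact group and says neither to whom nor how that group is matched. Sections 4.1 and 8.1 do not repeat it.

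**Contrasts.** The Endpoints row of the synopsis names "The diagnostic performance of retinal and choroidal thickness, flow index and vessel density to classify between amyloid positive vs amyloid negative" controls, followed by amyloid-positive vs amyloid-negative MCI, AD and DLBD. Section 5, item 6, repeats that the ability of the parameters to "classify between amyloid positive vs amyloid negative controls, amyloid-positive vs amyloid negative MCI, AD and DLBD will be evaluated".

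**Analysis.** Section 8.2 introduces the ROC and AUC analysis with "To evaluate the diagnostic performance of these parameters in distinguishing between subcategories" and names no covariate. Its only regression model is a logistic one for cardiovascular risk factors. On age and other demographics it says "Demographics and measured parameters will be analyzed with descriptive statistics". The threshold is general: "Statistical significance will be based on two-sided P-values of <0.05".

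**Data.** Section 10 says "Demographics and disease-related parameters (functional assessment, biochemistry and imaging) will be retrieved from the electronic medical health record", so age is available without a new procedure.

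**The concern.** The groups are not formed by randomisation. Under section 4.1, controls come from a community cohort, MCI patients from a memory-clinic cohort, and AD and LBD patients from the memory clinic. Section 3 itself treats age as something to balance, but only for one group. Three contrasts are left without stated matching:

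- amyloid-positive vs amyloid-negative controls (indirect at best, if both subgroups are matched to the same patients);
- amyloid-positive vs amyloid-negative MCI;
- AD vs LBD.

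If two groups differ in age and an OCT parameter varies with age, the AUC partly measures age rather than amyloid status or dementia subtype. A reader given only the raw AUC cannot separate the two. Diagnostic performance is a secondary objective of an exploratory study, but it is also what the Endpoints row names.

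**Working it through.** **Inputs from the protocol.** Section 8.1 gives 15 + 15 controls, 15 + 15 MCI, 15 AD and 10 LBD. The sum 15+15+15+15+15+10 = 85 agrees with the synopsis. No power calculation is stated, so there is no other figure to reproduce. The three contrasts above have sizes 15 vs 15, 15 vs 15 and 15 vs 10. The test level is two-sided 0.05.

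**Assumed inputs.** The protocol gives none of these: within-group age SD 7 years; correlation r between age and the OCT parameter 0.2–0.5; age gap 3, 5 or 8 years.

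**Step 1. How large a gap can chance produce?** The SD of the difference in mean age, in SD units, is √(1/n₁ + 1/n₂).
- 15 vs 15: √(2/15) = 0.365; 1.96 × 0.365 = 0.72 SD, or 0.72 × 7 ≈ 5.0 years.
- 15 vs 10: √(1/15 + 1/10) = 0.408; 1.96 × 0.408 = 0.80 SD, or 0.80 × 7 = 5.6 years.

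Gaps of 3–5 years therefore need no systematic cause. An 8-year gap would.

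**Step 2. AUC from age alone, no disease effect.** With normal distributions, AUC = Φ(r × gap / (7√2)), where 7√2 = 9.90.

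| Gap | r = 0.2 | r = 0.5 |
|---|---|---|
| 3 years | Φ(0.6/9.90) = 0.52 | Φ(1.5/9.90) = 0.56 |
| 5 years | Φ(1.0/9.90) = 0.54 | Φ(2.5/9.90) = 0.60 |
| 8 years | Φ(1.6/9.90) = 0.56 | Φ(4.0/9.90) = 0.66 |

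**Step 3. False-positive rate of the unadjusted test.** Mann-Whitney (AUC) test, no disease effect, simulated with 10,000 runs per setting, at 15 vs 15 and 15 vs 10 only.
- r 0.2–0.3, gap 3–5 years: about 5–8%.
- r 0.5, gap 5 years: 12–14%.
- r 0.5, gap 8 years: 30% at 15 vs 15 and 25% at 15 vs 10.

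**Step 4. Does adjustment remove the shift?** With no disease effect, the age-adjusted AUC averages 0.49–0.51. Its bootstrap interval, with the slope refitted in each resample, excludes 0.5 in 4–8% of runs, slightly too often at an 8-year gap. A linear model on group and age rejects in about 5% of runs (4.5–5.8%).

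**Step 5. What does adjustment cost?** The variance inflation of the group effect is 1 + p(1−p)(gap/7)², with p = n₁/(n₁+n₂). At 15 vs 15, p(1−p) = 0.25:
- 3 years: 1 + 0.25 × 0.184 = 1.05;
- 5 years: 1 + 0.25 × 0.510 = 1.13;
- 8 years: 1 + 0.25 × 1.306 = 1.33.

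Adjustment also removes the variance that age explains, so the net factor is the inflation times (1 − r²). At 3 years this is 1.00, 0.95 and 0.78 for r 0.2, 0.3 and 0.5; at 8 years it is 1.27, 1.21 and 1.00. The mean width of the 95% AUC interval at 15 vs 15, adjusted vs raw, is 0.45 vs 0.41 (r 0.3, 3 years) and 0.49 vs 0.39 (r 0.5, 8 years).

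**The case against.** The strongest reply is that this is ordinary content of a statistical analysis plan. Section 8.2 says that ROC/AUC will be used; it does not rule out adjustment, and a plan not available here may add it. That stands, and it is why the point ranks as an improvement only. What remains is that the protocol states a method and a scope of matching, and a better method is available at almost no cost.

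Second, the premises are assumed. The protocol gives no age gap and no age effect, and section 8.1 says that no distribution data exist for flow index or vessel density. The figures show what could happen, not what will. Both control subgroups come from one cohort, and so do both MCI subgroups, so a gap of 8 years there would need a systematic age difference by amyloid status that the protocol does not state.

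Third, sampling error dominates. A raw interval about 0.4 wide at 15 vs 15 exceeds the age shift at gaps up to 5 years. This also stands, and it limits the benefit. Describing demographics will show any age imbalance, but not how far it moves the AUC.

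A reader might infer error rates as high as 41%. That figure arises at 30 vs 15 with r 0.5 and an 8-year gap, a group size that belongs to none of the three contrasts listed here. A reader might also see a contradiction between the control ages in the synopsis (55–80) and in section 4.1 (55–85). The second is attached to the source cohort and the first to the enrolled controls, so both can be true. The ranges are not part of this point.

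**Conclusion.** The point holds as a cheap improvement. Age matching is stated for one group, without a comparator. Three contrasts are not covered, or are covered only indirectly, and the stated ROC analysis carries no age term. At small gaps and weak correlation the harm is slight: 5–8% false positives instead of 5%. It becomes material at r 0.5 and 5 years (12–14%) and large only in the extreme case of r 0.5 and 8 years (25–30%). All of these rest on an assumed age SD of 7 years, a linear age effect and normal distributions.

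A reader might go further and conclude that the protocol is wrong, contradicts its own promise of matching, or will produce AUCs confounded by age. The document supports none of these. It does not promise matching for the three contrasts, does not exclude adjustment, and gives no evidence that the groups differ in age or that the parameters depend on it.

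**What to change.** **Section 8.2.** Keep the raw AUC. Beside each one, report an age-adjusted AUC: subtract from the OCT value a pooled within-group age slope, and give a bootstrap 95% interval that refits the slope in every resample. Alternatively, test group in a linear model of the OCT parameter on group and age; this held its level better than the bootstrap interval at large gaps.

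**Section 3.** State which groups the controls are age-matched to, or delete the phrase.

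**Cost.** A few words and minor analysis work; no extra subjects, visits or tests. The price is precision when age and group are correlated. For an assumed 0.8 SD effect at 15 vs 15 and r 0.3, the power of the adjusted test is 58% with no gap, 56% at 3 years, 53% at 5 and 48% at 8. This loss, together with the wider AUC interval, is why the adjusted AUC should stand beside the raw one and not replace it.
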